## 1.3. Nonclinical Studies

#### 1.3.1. Pharmacology

Details of all nonclinical studies can be found in the Investigator's Brochure.

## 1.3.2. Juvenile Toxicity Study

Page 24 of 90 CONFIDENTIAL

## 1.4. Clinical Studies

20 1	
	26. 27. 3

Study EDP 938-101 evaluated the antiviral activity, PK, and safety of EDP-938 in healthy adult subjects inoculated with RSV-A Memphis 37b. The primary objective of this two-part study was to evaluate the antiviral activity of EDP-938 compared with placebo in healthy adult subjects inoculated with RSV-A Memphis 37b.

In Part 1 of Study EDP 938-101, 115 subjects were randomized to 1 of 3 treatment groups for 5 days of oral suspension dosing as follows: EDP-938 (500 mg loading dose [LD] followed by 300 mg BID every 12 hours for a total of 10 doses, n = 38); EDP-938 (600 mg QD followed by a placebo dosed at 12 hour intervals, for a total of 10 doses, n = 39); placebo (n = 38) every 12 hours. In Part 2 of Study EDP 938-101, 63 subjects were randomized into 1 of 3 treatment groups for 5 days of EDP-938 oral suspension with doses being informed by Part 1 data and dosing as follows: EDP-938 (400 mg LD followed by 200 mg BID for a total of 10 doses (n = 21), EDP-938 600 mg LD followed by 300 mg once a day followed by a placebo dosed at 12 hours interval, for a total of 10 doses (n = 21), placebo every 12 hours (n = 21).

In both Parts 1 and 2, all EDP-938 regimens yielded highly significantly lower RSV viral load AUCs than their placebo group (p<0.001) and robustly lowered 10-point RSV total symptom score AUCs compared to placebo. Results for active treatment groups were similar, with no indication that one regimen was better than the other in either Part 1 or Part 2.

Following administration, EDP-938 was rapidly absorbed with systemic EDP-938 exposures that were generally comparable to those observed in the first-in-human study at similar doses, and a half-life that supports QD or BID dosing. Following multiple dose administration, the geometric mean C24 ranged from approximately 14.5- to 40-fold higher than the in vitro EC90 for RSV M37 (20 ng/mL). There was no correlation between efficacy endpoints (viral load AUC and total symptom score) and exposure to EDP-938 (AUC).

All dose regimens were well tolerated. AEs were infrequent, generally mild, and all resolved. There were no serious or severe AEs and no AEs that led to discontinuation of study drug. In Part 1, headache, dizziness, and diarrhea were more common in 1 or both EDP-938 arms than in the placebo arm. In Part 2, nausea, dizziness, and upper respiratory tract infection were more common in 1 of the EDP-938 arms than in the placebo arm. In Part 1, all AEs in EDP-938 recipients were mild except for a single event of dyspepsia that was considered moderate. In Part 2, all AEs in EDP-938 recipients were mild except for a single event of moderate vessel puncture site paraesthesia. Results for physical examinations, ECGs, spirometry, and laboratory tests, including liver function tests and cardiac enzymes, showed no pattern of changes, and any changes observed were generally discrete and were broadly comparable among EDP-938 and placebo treatment groups.

In this Phase 2a study of healthy adults inoculated with RSV, all 4 EDP-938 regimens were well tolerated and demonstrated robust reductions in both RSV RNA viral load levels and total symptom scores as compared to placebo, with favorable PK profiles and safety profiles that were comparable to placebo.

Study EDP 938-102 was a Phase 2b, randomized, double-blind, placebo-controlled, multicenter study of EDP-938 administered orally for the treatment of acute upper respiratory tract infection due to RSV in ambulatory adult subjects.

Eighty-one subjects were randomized and received EDP-938 or matching placebo. In both treatment groups, 11 subjects had TEAEs. Most of the TEAEs were mild and not related to study drug. There were no deaths, other SAEs, or study discontinuations due to AEs. The safety profile was consistent with previous clinical studies in healthy subjects. EDP-938 exposures were consistent with those observed in subjects treated with EDP-938 in previous studies. The primary endpoint, total symptom score AUC from Day 1 through Day 14, was not met. The mean total symptom score AUC (days × score) was not statistically different between the 2 groups (p=0.246). Although the secondary antiviral endpoints were not met, a trend in favor of EDP-938 treatment group was observed with regard to the percentage of subjects achieving undetectable RSV RNA, with a statistically significant difference in favor of EDP-938 observed at the end of treatment at Day 5 (p=0.033).

#### **Potential Risks and Benefits** 1.5.

details about this study).

In clinical studies, EDP-938 has been safe and generally well tolerated, with AEs being infrequent, generally mild, and resolving in follow-up.

The safety profile of EDP-938 continues to evolve through ongoing clinical studies and consequently not all risks associated with EDP-938 exposure are known. Based on data from the approximately adults exposed to EDP-938 to date, no single safety event or pattern of events has been consistently identified to be associated with EDP-938 exposure and such reported AEs have been generally mild and occurring at a rate similar to placebo.

No serious adverse reactions are considered expected by the Sponsor for expedited reporting and identification of suspected unexpected serious adverse reactions in the Development Safety Update Report for EDP-938.

With regard to potential risks associated with trial participation, pediatric subjects enrolled to this study will undergo procedures including phlebotomy, ECG testing, and respiratory secretion sampling, (e.g., nasal swabs, that may cause discomfort to a child). Efforts have been made throughout the study to limit these procedures and, where possible, alternatives have been provided when such testing cannot readily be performed, such as heel sticks or finger sticks, and limited lead ECG testing. There is a requirement for repeated blood sampling throughout the study to monitor safety and PK. Efforts have been made to limit blood sample volumes as much as possible, e.g., screening may include assessment of recent laboratory tests, limiting blood draw frequencies and volumes and the provision of alternatives blood sampling methods as noted above.

# Additionally, to mitigate any risk to pediatric subjects enrolled to the trial the following will be undertaken:

- A Study Steering Committee (SSC) blinded to treatment assignment will ensure the continuing safety of subjects enrolled to the study through scheduled and as needed evaluations of data to inform dose selections and to review events that meet stopping rule criteria. See Section 4.2.1 for additional information about the SSC.
- An Independent Data Monitoring Committee (IDMC) unblinded to treatment assignment will ensure the safety of subjects enrolled to the study through reviews of safety data. See Section 4.2.2 for additional information about the IDMC.

This is the first study that will evaluate the safety, PK, and efficacy of EDP-938 in pediatric patients with RSV, and consequently, the efficacy and safety of EDP-938 in pediatric patients are not known. Because EDP-938 has previously demonstrated clinical efficacy in the adult healthy volunteer RSV challenge study, pediatric subjects enrolled to this trial may also experience a rapid clearance of RSV infection and a reduction in the symptoms associated with RSV infection compared to those who do not receive EDP-938. However, it is possible that no such effect will be observed. Additionally, since this is a placebo-controlled trial, pediatric subjects enrolled to the placebo arm will not be expected to derive any such benefit. Consequently, subjects enrolled to the trial may experience no benefit with regard to impacting the rate of clearance of RSV or resolution of symptoms associated with RSV infection.

## 2. OBJECTIVES AND ENDPOINTS

## 2.1. Objectives

The primary efficacy objective is to evaluate the antiviral activity of EDP-938 in the pooled population (subjects from Part 1 and Part 2 together).

## 2.1.1. Part 1: Primary and Secondary Objectives

#### **Primary Objectives**

- To evaluate the PK of EDP-938;
- To assess the safety and tolerability of EDP-938.

#### Secondary Objective

• To evaluate the antiviral activity of EDP-938.

## 2.1.2. Part 2 and Pooled Population: Primary and Secondary Objectives

#### **Primary Objective**

• To evaluate the antiviral activity of EDP-938.

#### Secondary Objectives

- To assess the safety and tolerability of EDP-938;
- To evaluate the PK of EDP-938.
- To evaluate additional antiviral activity measures of EDP-938.
- To evaluate clinical outcomes of EDP-938.

•

## 2.2. Endpoints

The primary efficacy endpoint is the daily change in RSV shedding in nasal swab samples determined using RT-qPCR from Baseline through the treatment phase in the pooled population (subjects from Part 1 and Part 2 together).

## 2.2.1. Part 1: Primary and Secondary Endpoints

## **Primary Endpoints**

- PK parameters of EDP-938 including AUC and predose concentrations;
- Safety and tolerability of EDP-938 compared to placebo as assessed by, but not limited to, AEs, vital signs, and clinical laboratory results.

## Secondary Endpoints

- AUC for RSV RNA viral load measured in nasal swab samples by quantitative reverse transcription polymerase chain reaction (RT-qPCR);
- Daily change in RSV shedding in nasal swab samples determined using RT-qPCR from Baseline through the treatment phase;
- Proportion of subjects with RSV RNA viral load below the limit of detection (LOD) in subjects receiving EDP-938 compared to placebo;
- Time to RSV RNA viral load being undetectable.

## 2.2.2. Part 2 and Pooled Population: Primary and Secondary Endpoints

## **Primary Endpoint**

Daily change in RSV shedding in nasal swab samples determined using RT-qPCR from baseline through the treatment phase.

## Secondary Endpoints

- Safety and tolerability of EDP-938 compared to placebo as assessed by, but not limited to, AEs, vital signs, and clinical laboratory results;
- AUC for RSV RNA viral load measured in nasal swab samples by RT-qPCR;
- Proportion of subjects with RSV RNA viral load below the LOD in subjects receiving EDP-938 compared to placebo;
- Time to RSV RNA viral load being undetectable;
- PK parameters of EDP-938 including AUC and predose concentrations;
- Time to discharge for hospitalized subjects;
- Time to use of oxygen for hospitalized subjects who are not receiving oxygen at the time they receive the first dose of study drug;

- Proportion of hospitalized subjects requiring oxygen supplementation or have an increased oxygen requirement;
- Time to mechanical ventilation for hospitalized subjects;
- Proportion of hospitalized subjects requiring mechanical ventilation;
- Deaths among hospitalized subjects;
- Time to hospitalization for initial outpatients who are subsequently hospitalized;
- Proportion of outpatients who are subsequently hospitalized or died;
- Time to resolution of symptoms for outpatients who are not hospitalized.

## **3. SELECTION OF SUBJECTS**

## 3.1. Subject Inclusion Criteria

Each subject must meet all of the following criteria to be enrolled into this study:

- Male or female who is either ≥6 months to ≤36 months (for Age Group 1) or ≥28 days to
  <6 months (for Age Group 2), defined at the time of randomization. Subjects in Age Group 2 must have been born ≥29 weeks of gestation to be eligible. If a subject was born

  <29 weeks of gestation, the subject can only be enrolled in Age Group 1;

- 2. Subjects diagnosed with RSV infection using an approved diagnostic assay, without known and/or documented coinfection with SARS-CoV-2. If RSV infection is not confirmed, caregivers may be asked to sign a RSV Diagnostic Test ICF allowing a rapid antigen RSV test to be performed;
- Subjects with signs of an acute respiratory illness (e.g., fever [or symptoms of fever], cough, nasal congestion, runny nose, rapid breathing, shortness of breath, or wheezing) with onset ≤7 days for Part 1 and ≤5 days for Part 2 before the time of signing the informed consent form (ICF);

Note: Time of onset of signs is defined as the caregiver(s) estimated time of awareness of the first sign of respiratory infection or worsening from the subject's pre-existing respiratory signs.

- 4. Have a calculated creatinine clearance rate not below the lower limit of normal (LLN) for the subject's age as determined by the Schwartz equation (Schwartz & Work, 2009) at Screening;
- 5. In the Investigator's opinion, the subject's caregiver understands and is able to comply with protocol requirements, instructions, and protocol-stated restrictions, and the subject is likely to complete the study as planned.

#### Additional inclusion criterion for Part 1 Cohort 1, Age Group 2

6. Subject is currently or is planned to be hospitalized as a consequence of RSV infection and is not anticipated to be discharged in less than 24 hours after enrollment.

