After the ICF is signed, screening assessments will be done, including physical examination, ECG, vital sign and body measurements. Some procedures performed as part of standard of care (such as an RSV diagnostic test or safety laboratory tests) may be used to determine study eligibility if they are performed within 72 hours of when the ICF is signed, as specified in the SoA. Screening safety laboratory test samples will be sent to the local laboratory for expedited testing.

Subjects who have symptom onset, defined as the estimated onset of the first sign of respiratory infection, that does not exceed 7 days for Part 1 and 5 days for Part 2 before the signing of the ICF by their caregiver and whose swab sample tests positive for RSV will undergo further screening procedures to determine study eligibility. Screening should be completed as soon as

possible to ensure that subjects will be randomized and administered the first dose of study drug within 24 hours of signing the ICF.

**Treatment Period (Days 1 to 5):** Subjects who are eligible for the study will be randomized 2:1 (Part 1) or 4:1 (Part 2) to EDP-938:placebo. Subjects will be considered enrolled at the time of randomization.

Nasal swab samples will be collected throughout the treatment period for RSV viral load assessments. At each scheduled visit, the site Investigator or designee will complete the Professional ReSVinet clinical scoring system.

The subjects' caregiver will receive an eCOA handheld device. This device will be used to complete the Parent/Guardian ReSVinet clinical scoring system beginning after randomization but before the first dose and subsequently QD at approximately the same time each day  $\pm 2$  hours. The palatability question should be completed postdose. The device should be brought to each site study visit.

The subjects' caregivers will receive instructions on the proper use and care of the eCOA device. If a caregiver is unable to use the eDiary, a paper diary may be used.

In a subset of subjects, the subjects' caregivers will also complete the clinical scoring system on paper after randomization but before the first dose and subsequently twice daily, approximately every 12 hours.

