## 4.1. Dose and Treatment Schedule

Approximately 90 subjects are planned to be enrolled. Oral doses of EDP-938 or placebo, will be administered OD. Initial doses are planned to

be 5 mg/kg in each age group:

- Group 1 (Ages  $\geq 6$  to  $\leq 36$  months);
- Group 2 (Ages  $\geq$  28 days to <6 months);

Varying age-appropriate volumes of a fixed concentration (**Constitution**) of EDP-938 or placebo will be administered to achieve the intended dose in each pediatric patient.

Subjects who meet all of the inclusion criteria and none of the exclusion criteria will be eligible to enter the study and will be randomized 2:1 (Part 1) or 4:1 (Part 2) to EDP-938:placebo.

The study design is shown in Figure 1.

## Part 1

Enrollment will begin simultaneously with Cohort 1 Age Group 1 and Cohort 1 Age Group 2. When at least 9 subjects have been randomized in Cohort 1, for each age group, the SSC will review available blinded data, including at least safety and PK data, and will determine dosing for Part 1 Cohort 2 for each age group. The SSC will meet as required to review emerging safety and PK data to support dose decision and initiation of Cohort 2. Enrollment in Cohort 1 age groups will continue until 12 subjects have been enrolled.

Cohort 1 Age Group 1 will include subjects who may be hospitalized or non-hospitalized at enrollment. Cohort 1 Age Group 2 will include subjects who are hospitalized at enrollment.

Clinical Study Protocol	
EDP 938-201	

Cohort 2 for both age groups will include subjects who may be hospitalized or non-hospitalized at enrollment.

Additional Part 1 cohorts may be added, as deemed necessary by the SSC.

## Part 2

Both age groups will include subjects who may be hospitalized or non-hospitalized at enrollment. The start of dosing for each age group will be contingent upon at least 6 subjects in that age group being exposed to EDP-938 in Part 1 Cohort 2 and will be based on SSC recommendations. After completion of dosing in the Part 2 cohort, the SSC will review available blinded data, including at least safety and PK data, in that age group. Twenty subjects are planned for each age group, but additional subjects may be enrolled based on SSC recommendations to allow a sufficient number of subjects to determine doses for both age ranges.

Additional Part 2 cohorts may be added, as deemed necessary by the SSC.

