- Time to confirmed undetectable RSV RNA viral load (days) is defined as the time between the date of first dose to the first 2 consecutive post-baseline time points of

achieving RSV RNA viral load TND. Subjects with baseline RSV viral load TND will be excluded from the analysis.

Frequency counts and percentages of subjects by end of study (Day  $28 \pm 4$ ), and their respective 95% CIs will be reported using Clopper Pearson CI methods for the following endpoints summarized using the Efficacy Population.

- Proportion of hospitalized subjects requiring oxygen supplementation or have an increased oxygen requirement.
  - Subjects who are hospitalized at randomization and/or during study are included. The
    proportion will be defined by the number of subjects who develop a new requirement for
    oxygen supplementation or new increase(s) in oxygen requirements after the first dose of
    study drug, based on the response of "yes" to the "is this an increase of oxygen
    supplementation compared to previous use?" question on the Oxygen Supplementation
    CRF.
- Proportion of hospitalized subjects requiring mechanical ventilation
  - Subjects who are hospitalized at randomization and/or during study are included. The proportion will be defined by the number of subjects who developed a new requirement for mechanical ventilation after the first dose of study drug. Subjects on mechanical ventilation prior to the first dose of study drug are excluded from analysis.
- Deaths among hospitalized subjects
  - Subjects who are hospitalized at randomization and/or during study are included.
- Proportion of outpatients who are subsequently hospitalized or died
  - $\circ$  Subjects who are not hospitalized at randomization are included.
- Proportion of outpatients who died
  - Subjects who are not hospitalized at randomization are included.

The following endpoints will be summarized using the Efficacy Population. The summary statistics will include, at a minimum, the number of non-missing measurements, mean, standard deviation, median, minimum, 25th percentile, 75th percentile, and maximum.

- Time to discharge for hospitalized subjects
  - Time to first hospital discharge for subjects who are hospitalized at randomization will be defined as the time between the first dose of study drug and the first date of discharge. For subjects with continuous hospitalization, the last date of discharge from the continuous hospitalization will be used.

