  - This analysis includes subjects who are hospitalized at randomization and required mechanical ventilation at any time after the first dose of study drug. The duration of mechanical ventilation (days) is defined as the sum of each duration of mechanical ventilation (days) that occurred from the first dose of study drug to the end of study. The duration of mechanical ventilation for the initial hospitalization is calculated as date/time of the end of mechanical ventilation date/time of first dose of study drug. The duration of mechanical ventilation for subsequent rehospitalization(s) is calculated as date/time of the end of mechanical ventilation date/time of the start of mechanical ventilation. Missing start times will be imputed to 00:01. Missing end times will be imputed to 23:59.
- Time to hospitalization for initial outpatients who are subsequently hospitalized
  - Time to hospitalization for initial outpatients who are subsequently hospitalized will be calculated, defined as the time between the date/time of first dose to the first date of hospitalization.
- Time to resolution of symptoms for outpatients who are not hospitalized
  - Time to resolution of symptoms for outpatients at randomization who are not hospitalized during study, is defined as the time between the date/time of first dose to the first of 2 consecutive time points where each of the seven symptoms assessed by the Parent/Caregiver ReSVinet clinical scoring is 0 or 1. If a subject meets the resolution

definition (0 or 1 score for 2 consecutive timepoints) at baseline and Day 2, then this subject will be excluded from the analysis.

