# 4.13.5 Efficacy Analysis for Pooled Population

The primary endpoint is the daily change in RSV shedding in nasal swab samples determined using RTqPCR from baseline through the treatment phase in the pooled population (subjects from Parts 1 and 2 together).

All secondary efficacy endpoints described in *Section 4.13.4*, as well as all exploratory endpoints described in Section 4.13.7 are also the secondary and exploratory endpoints for the pooled population and will be analyzed with the pooled data from both Parts 1 and 2.

All pooled efficacy data will be summarized descriptively by EDP 938 and Placebo for each age group and combined EDP 938 and Placebo, as described in *Section 4.13.4* and *Section 4.13.7*.

Inferential statistics analysis will be performed to detect treatment effects of EDP 938 and Placebo using the Efficacy Population, mITT-3 and mITT-5 for the following RSV RNA viral endpoints as well as RSV symptom related endpoints described in *Section 4.13.7* (except for RESOLVE-P where Efficacy Population is used)

- Daily change in RSV shedding in nasal swab samples determined using RT-qPCR from baseline through treatment phase
  - Absolute change from baseline in RSV RNA viral load (outcome variable) will also be analyzed using MMRM as described below.
  - AUC for RSV RNA viral load measured in nasal swab samples by quantitative reverse transcription polymerase chain reaction (RT-qPCR) will be estimated via MMRM.
- Time to RSV RNA viral load being undetectable

Time to RSV RNA viral load being undetectable (TND) will be analyzed using two approaches as defined below:

- Time to RSV RNA viral load being undetectable (days) is defined as the time between the date of first dose to the first date during post-dose period of achieving RSV RNA viral load TND after which no further samples have detectable RSV RNA viral load. Subjects with baseline RSV viral load TND will be excluded from the analysis.
- Time to confirmed undetectable RSV RNA viral load (days) is defined as the time between the date of first dose to the first of 2 consecutive post-baseline time points of achieving RSV RNA viral load TND. Subjects with baseline RSV viral load TND will be excluded from the analysis.

Inferential statistics analysis approaches are as follows:

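### An infant enrolled under criterion 6 with admission only planned would count as an outpatient later hospitalized in the pooled secondary endpoints, because the SAP classifies by status at randomization

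*Protocol*

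**What the plan says.** **Entry.** Protocol 3.1 gives criterion 6 under the title "Additional inclusion criterion for Part 1 Cohort 1, Age Group 2". It is met if the "Subject is currently or is planned to be hospitalized as a consequence of RSV infection", provided discharge is not expected within 24 hours of enrollment. No other cohort has this criterion.

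**Design text.** Protocol 4.1 says "Cohort 1 Age Group 2 will include subjects who are hospitalized at enrollment", and SAP 2.1 says the same. The Protocol Summary fixes the time point: "Subjects will be considered enrolled at the time of randomization".

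**Outpatient endpoints.** SAP 4.13.4 lists "Proportion of outpatients who are subsequently hospitalized or died" and defines its population in one line: "Subjects who are not hospitalized at randomization are included". It also states: "Time to hospitalization for initial outpatients who are subsequently hospitalized will be calculated", measured from first dose. Neither entry makes an exception for an admission already planned.

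**Inpatient endpoints.** In the same section, time to discharge, time to oxygen and time to mechanical ventilation are limited to subjects hospitalized at randomization. The oxygen and ventilation proportions and deaths also take subjects hospitalized later in the study.

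**Pooling.** Part 1 has no hospitalization endpoint of its own. Under SAP 4.13.5 the Part 2 secondary endpoints "will be analyzed with the pooled data from both Parts 1 and 2", and that brings Cohort 1 infants into them.

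**The concern.** Criterion 6 lets in an infant who has not yet been admitted, and screening, randomization and first dose are meant to fall within 24 hours of consent. Dosing before the admission takes place is therefore possible under the criterion as written. The SAP's rule would then make that infant an outpatient and record the admission as a later hospitalization, although it was planned before any study drug was given and treatment could not have prevented it.

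Three results would be affected. The outpatient admission proportion would contain events that carry no information about the drug. Time to hospitalization would contain values near zero. And one child would be an outpatient with an event, a member of the inpatient proportions, and absent from the matching inpatient times. Protocol 9.1.2 sets planned admissions for pre-existing illness aside for adverse events, unless the condition worsens unexpectedly; the efficacy endpoints have no matching rule.

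**Working it through.** **1. Planned size.** SAP 4.2 gives 12 subjects per cohort and age group in Part 1 and 20 per age group in Part 2: 2 × (12 + 12) + 2 × 20 = 88. This agrees with the stated figure of approximately 90.

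**2. Pooled arms.** Part 1 is 2:1, so each of its four cohort-by-age-group cells is 8:4. Part 2 is 4:1, so each of its two cells is 16:4.
- EDP-938: 4 × 8 + 2 × 16 = 64
- Placebo: 4 × 4 + 2 × 4 = 24

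**3. Reach of criterion 6.** It covers one cell, 8 EDP-938 and 4 placebo.
- All subjects pooled: 8/64 = 12.5% of EDP-938 and 4/24 = 16.7% of placebo.
- Age Group 2 pooled (SAP 4.13.5 also reports by age group): 8/(8 + 8 + 16) = 8/32 = 25.0% and 4/(4 + 4 + 4) = 4/12 = 33.3%.

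**4. One infant traced through SAP 4.13.4.** Take an infant eligible under criterion 6, randomized and dosed, then admitted as planned.

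| Endpoint | Population rule | Result for this infant |
|---|---|---|
| Outpatients hospitalized or died | Not hospitalized at randomization | Included, with an event |
| Time to hospitalization | Initial outpatients later hospitalized | Included, near zero |
| Time to discharge, oxygen, ventilation | Hospitalized at randomization | Left out |
| Oxygen and ventilation proportions, deaths | Hospitalized at randomization or later | Included |

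**5. Direction.** Let f be the share of criterion 6 infants not yet admitted at randomization, and q the share of outpatients among everyone else (64 − 8 = 56 EDP-938, 24 − 4 = 20 placebo), both equal across arms. With no other admissions, the expected event rates are:
- EDP-938: 8f / (56q + 8f) = f / (7q + f)
- Placebo: 4f / (20q + 4f) = f / (5q + f)

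The placebo rate is higher for any f and q above zero. The cause is the allocation: criterion 6 infants are split 2:1, while the remaining subjects are split 56:20 = 2.8:1.

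**6. Illustration.** The documents give neither f nor q, so both are assumed. With f = 0.5 and q = 0.5 and no other admissions:
- EDP-938: 4/(28 + 4) = 4/32 = 12.5% (Clopper-Pearson 95% CI 3.5% to 29.0%)
- Placebo: 2/(10 + 2) = 2/12 = 16.7% (2.1% to 48.4%)
- Planned admissions set aside: 0/28 and 0/10

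With f from 25% to 100%, q from 25% to 75%, and a true later admission rate of 0% to 5% in both arms, the EDP-938 minus placebo difference runs from −1.6 to −8.1 percentage points with no drug effect. If every infant is admitted before randomization (f = 0), it is zero.

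**The case against.** The strongest reply is that the problem needs one of two conflicting readings. The design text says this cohort is hospitalized at enrollment, and Protocol 4.4.1 treats hospitalization as a requirement, so that dosing is supervised. Planned admission could then describe status at screening, with the child admitted by randomization, and no criterion 6 infant would enter an outpatient denominator. This stands as a limit: the misclassification is conditional. It does not remove the point, because criterion 6 as written does not require admission by randomization and the SAP has no rule for the case it allows.

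It also stands that the consequence is limited. The endpoints are secondary and reached only through pooling. SAP 4.13.5 names viral RNA and symptom endpoints for inferential analysis, not the admission proportions.

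Four stronger conclusions might be inferred and are not supported:
- **That the false events work against EDP-938, because about two in three fall on that arm.** This is true of the expected count but ignores the denominators. EDP-938 is 64/88 = 73% of the pooled population, so the expected rates tilt the other way.
- **That the admission count is inflated by a definite percentage.** The documents give no share of unadmitted infants, no number of outpatients and no outpatient admission rate.
- **That the same holds in every cohort.** No other cohort has a planned-admission criterion. Showing it elsewhere would need the time of the decision to admit, which Protocol 8.9 does not list among the items collected.
- **That these infants are lost to the inpatient analyses altogether.** They stay in the oxygen, ventilation and death proportions.

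**Conclusion.** The point holds in a limited form. Criterion 6 conflicts with Protocol 4.1 and SAP 2.1. Under criterion 6 as written, the SAP's status-at-randomization rule gives a wrong classification for an infant randomized before a planned admission. At most 12 of 88 planned subjects are exposed, and the number actually affected could be anything from 0 to 12.

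The expected tilt in the crude pooled admission rate favors EDP-938. That direction rests on 2:1 allocation in every Part 1 cohort and on equal unadmitted and outpatient shares across arms; with so few infants, chance could produce a different split. The percentage-point figures are illustrations from assumed inputs. The documents do not call these events treatment failures; they are events in a secondary endpoint that is summarized descriptively. The primary viral-load analysis is unaffected.

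**What to change.** 1. In SAP 4.13.4, carried into 4.13.5, state that all infants enrolled under criterion 6 are classified as hospitalized at baseline for the inpatient and outpatient endpoints. Their time-to-event endpoints start at first dose, as for other inpatients, and their planned initial admission is not counted as an outpatient hospitalization. Say also how an infant whose planned admission never takes place is handled, since that child would have no discharge date.
2. Reconcile criterion 6 (Protocol 3.1 and the Protocol Summary) with Protocol 4.1 and SAP 2.1, so that all describe the same cohort.

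The cost is a short SAP definition and a wording correction. The infants can be identified by cohort and age group, so no new data or procedure is needed. SAP 4.13.6 already names final selected doses, which suggests that Cohort 1 enrollment may be over. If so, the SAP sentence is the part that still changes the results, and it should be in place before unblinding.
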